APPENDIX V HANDLING MISSING DATE

Prior/Concomitant medication:

Missing or partial medication start date:

- If only day is missing, use the first day of the month.
- If day and month are both missing, use the first day of the year.
- If day, month and year are all missing, use a date before the first dose date (in practice, use Jan. 01, 2000 to impute).

Missing or partial medication stop date:

- If only day is missing, use the last day of the month.
- If day and month are both missing, use the last day of the year.
- If day, month and year are all missing, assign 'continuing' status to stop date (in practice, use Dec. 31, 2050 to impute).

Adverse Event:

Imputation of missing AE start date:

- If AE start date is completely missing and AE end date is after the first dose date in Part A Period 1 but before first dose date in Part B, then use the first dose date in Part A Period 1 as the AE start date and classify the AE as a TEAE; if the AE end date is after the first dose date in Part B then
 - 1) Use the first dose date in Part A Period 1 as the AE start date
 - 2) Use the first dose date in Part B as the AE start date.
- If AE start date is completely missing, and AE end date is before the first dose date in Part A Period 1, then the AE is not a TEAE.
- If both AE start date and AE end date are completely missing then
 - 1) Use the first dose date as AE start date in Part A Period 1 and classify the AE as a TEAE for Part A
 - 2) Use the first dose date as AE start date in Part B and classify the AE as a TEAE for Part B

1006696
Parion Sciences Incorporated
CLEAN-PCD
SAP Version 1.0

Statistical Analysis Plan

- If only day is missing, use the first day of the month or the first dose date whichever is later, unless the AE start month is before the first dose date in which case, the AE start date remains missing and this AE is not a TEAE.
- If day and month are both missing, use the first day of the year or the first dose date whichever is later, unless the AE start year is before the first dose date. In this case, the AE start date remains missing and this AE is not a TEAE.

Imputed AE start date must be earlier than the original AE end date, otherwise set imputed start date = original AE end date and the AE is not a TEAE.

Missing AE causality

For summary tables of related AEs, report missing causality as 'related'.

Missing AE Severity

[figure not shown]
There will be no imputation of missing AE severity.

Missing SAE category

There will be no imputation of missing SAE category.

1006696
 Parion Sciences Incorporated
 CLEAN-PCD
 SAP Version 1.0

Statistical Analysis Plan

APPENDIX VI VISIT WINDOWS

The unscheduled or early withdrawal visit will be mapped to a scheduled visit for analysis using the date of collection/assessment as a basis to determine study day and then study day will be mapped to the intended visit. Table 8 and Table 9 below contain the analysis visit windows.

Table 8. Study windows

Study Period	Scheduled Visit/Day	Study Day Window	Analysis Visit
Period 1	Day 15 Visit	Day >1 - ≤ 22	Day 15
	Day 29 Visit	Day >22 - ≤ 36	Day 29
Period 2	Day 71 Visit	Period 2, Day >1 - ≤ 22	Day 15
	Day 85 Visit	Period 2, Day >22 - ≤ 36 ^a	Day 29
Period 3	Day 99 Visit	Period 3, Day >1 - ≤ 22	Day 15
	Day 113 Visit	Period 3, Day >22 - ≤ 36	Day 29

a: all assessments should happen before Part B dosing time.

For SGRQ, QOL-PCD [REDACTED] hematology, height and weight, [REDACTED] the following windows will be used:

Table 9. Study windows for Day 1 and Day 29 only

Study Period	Scheduled Visit/Day	Study Day Window	Analysis Visit
Period 1	Day 29 Visit	Day >1 - ≤ 36	Day 29
Period 2	Day 85 Visit	Period 2, Day >1 - ≤ 36 ^a	Day 29
Period 3 ^b	Day 113 Visit	Period 3, Day >1	Day 29

a: all assessments should happen before Part B dosing time.

[figure not shown]
b: visit windows for height and weight will only be applied for Period 1 and 2. Height and weight visit windows for Period 3 will be the same as table 6.

Once analysis visit windows are assigned, all visits, including scheduled visits, unscheduled visits, and early termination visits will be eligible for being flagged as the “analyzed record” within the analysis visit window. Note that the scheduled visit should match with the visit for which the visit window is defined. For example: If Day 29 visit falls in the visit window for Day 15, then Day 15 will be assigned to this visit. If no numerical measurement is available within a visit window, the measurement will be considered missing for the visit.

A subject’s individual analysis visit window could potentially contain more than one visit. In the event of multiple visits falling within an analysis visit window or in case of a

1006696
Parion Sciences Incorporated
CLEAN-PCD
SAP Version 1.0

Statistical Analysis Plan

tie, the following rules will be used in sequence to determine the “analyzed record” for the analysis visit window:

- the data closest to the scheduled day will be used.
- If there are multiple measurements with the same distance from the target day, the latest measurement will be used.

The data not flagged as the “analyzed record” will only be listed in subject listings.

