| Safety telephone call g      |  | X                                      | X  |   |   |   | X                           | X                                       |  |   | X   | X                           | X                           |  |  |                               |
| Inclusion/exclusion criteria review     | X  |  |  |   |   |   |                             |   |  |   |   |                             |                             |  |  |                               |
| Randomization h              | X  |  |  |   |   |   |                             |   |  |   |   |                             |                             |  |  |                               |
| Medical history                         | X  |  |  |   |   |   |                             |   |  |   |   |                             |                             |  |  |                               |
| QOL-PCD i                    | X  |  |  |   | X   | X   |                             |   | X  |   |   |                             |                             |  |  | X                             |
| SGRQ i                       | X  |  |  |   | X   | X   |                             |   | X  |   |   |                             |                             |  |  | X                             |

a Subjects will sign a new ICF (or assent if applicable) before the Day 85 Visit in order to continue into Treatment Period 3. If the subject does not sign the new ICF, Treatment Period 2 will end at Day 85 and the subject will continue through to the Safety Follow-up Telephone Call.

b Day 15, Day 71, and Day 99 clinic visit required for subjects randomized prior to IDMC approval to change visit to a telephone call.

c At the Day 85 Visit, subjects will remain in clinic for a total of 2 to 4 hours after dosing with study drug. The duration of the extended time for each subject (2 to 4 hours) will be left up to the discretion of the investigator. Post-dose safety assessments will be done prior to discharge from the clinic.

d Day 99 Visit or telephone call may occur any time between Day 88 and Day 99. The clinic visit may be changed to a telephone call after approval from the IDMC.

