#### **Subjects randomized prior to Independent Data Monitoring Committed (IDMC) approval to convert Day 15 Visit to a telephone call:**

- If a subject reaches the Day 15 Visit prior to IDMC approval to convert the Day 15 Visit to a telephone call, the Day 15 Visit must be completed to assess safety parameters, including AEs, vital signs, pulse oximetry, ECG, physical exam, clinical laboratory values, and spirometry. No telephone call is required on this day if a visit is conducted.
- If the IDMC does not approve to convert the Day 15 Visit to a telephone call, subjects will proceed as per the bullet above.

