**Subjects randomized after IDMC approval to convert Day 15 Visit to a Telephone Call:**

- The Day 15 Visit will be changed to a Day 15 Telephone Call to assess AEs. No visit is required on this day if a telephone call is conducted.

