8.1 PRIMARY EFFICACY ENDPOINT AND ANALYSIS

Part A

The primary efficacy endpoint for Part A is the absolute change in ppFEV1 from study baseline, after 28 days of treatment in each Treatment Period of Part A.

The null hypotheses to be tested are that the mean absolute change from study baseline in ppFEV1 after 28 days of treatment is the same for 1) VX-371 in HS versus placebo; 2) VX-371 versus placebo; 3) VX-371 in HS versus HS alone. The primary assessment of efficacy will be based on the comparison of VX-371 in HS versus HS alone.

[figure not shown]
The primary efficacy analysis is based on a mixed-effects model. This model will include the absolute change from study baseline in ppFEV1 after 28 days (Visit Day 29 for Period 1 and Day 85 for Period 2) of treatment as the dependent variable, treatment and period as fixed effects, study baseline as a covariate, and subject as a random effect. The within-subject covariance will be assumed to have the compound symmetry (CS) structure. Denominator degrees of freedom for the F-test for fixed effects will be estimated using the Kenward-Roger approximation. No imputation of missing data will be done.

The estimated mean of the dependent variable, a 95% CI, and a 2-sided p-value will be provided for each treatment. There will be no adjustment for multiplicity. Similarly, the estimated between-treatment differences along with the corresponding 95% CI and 2-sided p-values will be presented.

[figure not shown]
A sample SAS code is provided below:

1006696
Parion Sciences Incorporated
CLEAN-PCD
SAP Version 1.0

Waterfall plot of the change from study baseline in ppFEV1 at Day 29 will be plotted by treatment group.

[figure not shown]

Summary statistics for the actual values and absolute changes from study baseline in pre-dose ppFEV1 will be summarized descriptively by treatment and visit based on Part A FAS.

In addition, the actual values and absolute changes at post-HS screening from pre-HS screening visit as well as actual values and absolute changes at Day 1 post-dose from Day 1 pre-dose in each period will be summarized based on Part A Safety Set and Part B Safety Set.

1006696
Parion Sciences Incorporated
CLEAN-PCD
SAP Version 1.0

[Redacted text block consisting of multiple lines of blacked-out content]

Part B

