10.6 SPIROMETRY

Spirometry data in Part A and Part B will be summarized based on the Part A Safety Set and Part B Safety Set respectively. This will include the number and percentage of subjects at each scheduled time point relative to Part A period baseline value and Part B Baseline value for the following:

- Subjects with ≥ 10 percentage point decrease in ppFEV1
- Subjects with ≥ 15 percentage point decrease in ppFEV1
- Subjects with ≥ 20 percentage point decrease in ppFEV1

1006696
 Parion Sciences Incorporated
 CLEAN-PCD
 SAP Version 1.0

- Subjects with ≥ 0.2 L decrease in FEV1

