13.1.5.2 Table Conventions

- Units will be included where available
- If the categories of a parameter are ordered, then all categories between the maximum and minimum category should be presented in the table, even if n=0 for all treatment groups in a given category that is between the minimum and maximum level for that parameter. For example, the frequency distribution for symptom severity would appear as:

Severity Rating	N
severe	0
moderate	8
mild	3

Where percentages are presented in these tables, zero percentages will not be presented and so any counts of 0 will be presented as 0 and not as 0 (0%).

- If the categories are not ordered (e.g., Medical History etc.), then only those categories for which there is at least 1 subject represented in 1 or more groups should be included.

[figure not shown]

1006696

Parion Sciences Incorporated

CLEAN-PCD

SAP Version 1.0

- An Unknown or Missing category should be added to any parameter for which information is not available for 1 or more subjects.
- P-values should be output in the format: “0.xxxx”, where xxxx is the value rounded to 4 decimal places. Any p-value less than 0.0001 will be presented as <0.0001. If the p-value is returned as >0.9999 then present as >0.9999
- Percentage values should be printed to one decimal places, in parentheses with no spaces, one space after the count (e.g., 7 (12.1%), 13 (5.3%)). Unless otherwise noted, for all percentages, the number of subjects in the analysis set for the treatment group who have an observation will be the denominator. Percentages equating to 100% should be presented as 100%, without any decimal places.

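### If the mid-period clinic visit becomes a telephone call, the SAP's Day 15 by-visit rows mix routine visits with a selected set of unscheduled and early-termination readings

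*SAP*

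**What the plan says.** **The visit.** Protocol Table 3-2, footnote b, reads: "Day 15, Day 71, and Day 99 clinic visit required for subjects randomized prior to IDMC approval to change visit to a telephone call". For subjects randomized after approval, protocol section 8.1.3.1.1 says: "The Day 15 Visit will be changed to a Day 15 Telephone Call to assess AEs". Sections 8.1.3.1.3 and 8.1.3.2.1 do the same for Days 71 and 99. The change is conditional: "If the IDMC does not approve to convert the Day 15 Visit to a telephone call, subjects will proceed as per the bullet above". SAP section 2.2 reports that IDMC meetings have taken place, but neither document says whether or when the change was approved.

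**The analysis rule.** SAP Appendix VI says: "The unscheduled or early withdrawal visit will be mapped to a scheduled visit for analysis using the date of collection/assessment as a basis". Table 8 defines a Day 15 analysis visit in all three periods, running from after period Day 1 to period Day 22 inclusive. Scheduled, unscheduled and early-termination visits can all supply the analyzed record. The record nearest the scheduled day is used. A Day 29 visit held early enough to fall in the Day 15 window is assigned to Day 15.

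**The outputs.** SAP section 8.1 plans ppFEV1 values and changes that "will be summarized descriptively by treatment and visit based on Part A FAS". Section 10.6 counts falls in ppFEV1 and FEV1: "This will include the number and percentage of subjects at each scheduled time point relative to Part A period baseline value". Sections 10.2 to 10.4 and 10.7 summarize chemistry, vital signs, ECG and oximetry by scheduled visit or time point. Unless otherwise noted, for percentages "the number of subjects in the analysis set for the treatment group who have an observation will be the denominator" (section 13.1.5.2).

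Nothing in the public text limits the Day 15 row to subjects who had a scheduled mid-period visit, or splits it by whether that visit was a clinic visit or a call.

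**The concern.** A by-visit row is normally read as the state of the treated group at that time. That holds when everyone is due an assessment and absences are few. For a subject whose mid-period contact is a call, no reading is due. A reading on those days exists mainly because something prompted a visit or because treatment stopped. With subjects who have an observation as the denominator, post-switch subjects without such a reading drop out of the row.

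The Day 15 rows could then show lower ppFEV1 and a higher proportion with a marked fall than the treated group really had. A Day 15 to Day 29 comparison would set a small, partly selected group against nearly all subjects who completed the period. Spirometry, laboratory values, ECG, vital signs and oximetry are named among the primary safety endpoints, so the affected tables will be read.

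**Working it through.** The plan gives no figure on this point to reproduce. The check is window arithmetic, followed by an illustration.

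**1. Windows, in period days.**
- Day 15 clinic visit, plus or minus 3 days (protocol Table 3-2): Days 12 to 18.
- Day 15 analysis window (SAP Table 8): Days 2 to 22, which is 22 − 2 + 1 = 21 days.
- Day 29 visit, plus or minus 3 days: Days 26 to 32. To fall in the Day 15 window it must be held by Day 22, at least 26 − 22 = 4 days before its own window opens.

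**2. Who can enter the row after the switch.** The call yields adverse-event information and no measurement. A Day 29 visit inside its window cannot reach the row. Three routes remain: an unscheduled visit, an early-termination visit, or a Day 29 visit at least 4 days too early.

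**3. Why these entries are selected.** Protocol section 8.1.6 gives the purposes of unscheduled visits as extra safety assessment and follow-up of changes in clinical status or of findings. Section 8.1.3.1.1 lets the Day 4 safety call bring a subject back for a new medical problem. Section 9.5 lists a relative ppFEV1 decline of at least 15% among the reasons for which study drug may be withdrawn, and the early-termination visit includes spirometry (Table 3-3). Some of the variables that prompt a visit are the ones tabulated.

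**4. Table 9 beside Table 8.** Hematology, SGRQ and QOL-PCD have no scheduled mid-period assessment, and Table 9 gives them no Day 15 row. Table 8 does not apply the same logic to subjects who lose the mid-period visit.

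**5. Illustration of size.** Let *p* be the share of subjects who are post-switch and *u* the share with an unscheduled or early-termination reading in the window. Assume 95% attendance at scheduled visits and a mean ppFEV1 change 5 points lower for the non-scheduled readings. None of these four inputs is in the documents. Per 100 subjects:

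- scheduled readings: S = 100 × (1 − p) × 0.95
- non-scheduled readings: U = 100 × (1 − p) × 0.05 × u + 100 × p × u
- share of the row: U / (S + U); shift of the row mean: −5 × share

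For p = 0.50 and u = 0.05: S = 47.5, U = 0.125 + 2.5 = 2.625, share = 2.625 / 50.125 = 5.2%, shift = −0.26.

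| Post-switch share *p* | Non-scheduled share of row, *u* = 5% to 20% | Shift of row mean (points) |
|---|---|---|
| 25% | 2% to 8% | −0.1 to −0.4 |
| 50% | 5% to 18% | −0.3 to −0.9 |
| 75% | 14% to 39% | −0.7 to −2.0 |
| 90% | 32% to 66% | −1.6 to −3.3 |

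**6. Effect on the fall percentages, under a second set of assumptions.** Take 30% of subjects with a routine visit, 5% of the rest with a non-scheduled reading, means of 0 and −8 points, and an SD of 7 (the plan's sample-size SD). The non-scheduled share is 0.70 × 0.05 / (0.30 + 0.035) = 10.4%, and the row mean is −8 × 0.104 = −0.84. A fall of at least 10 points has probability Φ(−10/7) = 7.7% at a routine visit and Φ(−2/7) = 38.8% at the others. The row therefore shows 0.896 × 7.7% + 0.104 × 38.8% = 10.9%, against 7.7%.

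**The case against.** The strongest reply is that little depends on this row. The primary model uses only Day 29 and Day 85 (SAP section 8.1), and SGRQ, QOL-PCD and hematology have no Day 15 row. What remains is descriptive, with no test or decision rule attached. The switch may never have been approved. Unscheduled visits need not include spirometry. The record nearest the scheduled day is used, so a routine visit held on time normally takes precedence. All of this stands and limits the consequence. It does not supply a rule for the subjects who have no routine visit.

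The sizes above rest on inputs from outside the documents, and that also stands. Even a known approval date would not settle the numbers. Footnote b keeps the clinic visit for everyone randomized before approval, whereas the bullets in sections 8.1.3.1.1, 8.1.3.1.3 and 8.1.3.2.1 require it of subjects who reach it before approval.

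A reader might infer that the extra clinic visit also distorts the counts of subjects with at least one threshold abnormality. The documents do not support adding that here. Those counts cover the treatment-emergent period (SAP sections 10.2 to 10.4), not the Table 8 windows. Subjects are randomized concurrently in a 2:2:1:1 ratio, so unequal numbers of assessments should fall about evenly across arms.

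The Part B timing is also a separate matter. The protocol openly allows that "Day 99 Visit or telephone call may occur any time between Day 88 and Day 99", nominally period Days 4 to 15.

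One objection changes the remedy. Section 10.6 counts ppFEV1 and FEV1 falls only at scheduled time points. Simply removing non-scheduled readings from the Day 15 row would take those falls out of the safety tables.

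**Conclusion.** The point holds as a conditional one. If the IDMC approves the change, the Day 15 rows for ppFEV1, safety spirometry, chemistry, ECG, vital signs and oximetry are partly a selected sample and should not be read against Day 29. The likely direction for ppFEV1 is downward. In the illustration the shift runs from about 0.1 points (25% post-switch, 5% with a reading) to 3.3 points (90% and 20%). It rests on the assumed attendance, reading rate and 5-point deficit, and on a switch date that the documents do not give.

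Three stronger readings are tempting, and the documents support none of them:
- **The row consists only of problem visits.** The table pools all subjects, including those with routine pre-switch visits. Early termination can be at the subject's own request or for administrative reasons (protocol section 9.5), and a very early Day 29 visit can also land in the row.
- **The switch took place.** The protocol keeps the clinic visits if approval is withheld.
- **The efficacy conclusion or the comparison of arms is biased.** The primary analysis does not use the row. A difference between arms would need unequal rates of non-scheduled readings, which the documents do not show.

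**What to change.** 1. **SAP Appendix VI, with sections 8.1, 10.2 to 10.4, 10.6 and 10.7.** Build the Day 15 by-visit row only from scheduled Day 15, 71 and 99 clinic visits that were held, with subjects who had that visit as the denominator. Show Day 29 for the same subset beside it.
2. **SAP section 10.6.** At the same time, add a count of subjects with each listed fall (at least 10, 15 and 20 points in ppFEV1, and at least 0.2 L in FEV1) at any time in the treatment-emergent period, including unscheduled and early-termination readings. No tolerability event then leaves the safety tables.
3. **Any-time summaries.** Keep the non-scheduled readings in the existing treatment-emergent threshold counts and in the listings. The closing sentence of Appendix VI sends records not flagged as analyzed to listings only. It should be limited to the by-visit tables so that it does not exclude these readings from the counts.
4. **Transparency.** State in the SAP whether and when the IDMC approved the change for each visit.

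The cost is SAP wording, one flag for whether the mid-period clinic visit was held, and one added table. The Day 15 rows will contain fewer subjects. The primary analysis and data collection do not change.

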### 8.1.5 Early Termination of Treatment

If the subject prematurely discontinues study drug treatment, an ETT Visit should be scheduled as soon as possible after the subject decides to terminate study drug treatment. Subjects who prematurely discontinue treatment will also be required to complete the Safety Follow-up Telephone Call, approximately 28 days ( $\pm$  7 days) after their last dose of study drug.

If the subject withdraws consent for the study, no further evaluations will be performed, and no additional data will be collected. Parion Sciences may retain and continue to use any data collected before such withdrawal of consent.

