### 8.2.3 Rationale for Study Assessments

**Spirometry:** Spirometry (as measured by FEV1) is the most widely implemented standardized assessment to evaluate lung function. FEV1 obtained from spirometry is a reflection of the extent of airway obstruction and, as the most clinically accepted measure of disease progression in CF, indicates that FEV1 may be an equally acceptable measure in efficacy studies of the PCD population.

**QOL-PCD:** The QOL-PCD is a subject-completed, disease-specific instrument designed to measure impact on overall health, daily life, perceived well-being and symptoms that has been developed specifically for use in subjects with a diagnosis of PCD.

**SGRQ:** The SGRQ is a 50-item questionnaire with 76 weighted responses. This questionnaire measures health status (quality of life) in patients with diseases of airway obstruction. It has good discriminative and evaluative properties and is responsive to therapeutic trials.

The items in the SGRQ are divided into 3 domains: “Symptoms,” which is concerned with frequency and severity of respiratory symptoms; “Activity,” which is concerned with activities that cause or are limited by breathlessness; and “Impacts,” which covers aspects concerned with social functioning and psychological troubles resulting from airway disease. A score will be calculated for each domain and a total score will also be calculated. For each domain and for the total score, the range of values is 0 to 100, with higher values corresponding with greater impairment of quality of life. A minimum change in score of 4 units was established as clinically relevant after patient and clinician testing.

[REDACTED]

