3.5.1 Part A

The primary efficacy objective of Part A of this study is to evaluate the efficacy of VX-371 with and without HS in subjects ≥ 12 years of age with PCD. For efficacy analysis, the statistical inferences will be based on change from study baseline. The null hypotheses to be tested are that the mean absolute change from study baseline in ppFEV1 after 28 days of treatment is the same for 1) VX-371 in HS versus placebo; 2) VX-371 versus placebo; and 3) VX-371 in HS versus HS alone.

To have a feasible sample size and study duration, a crossover design has been proposed for Part A of this study. Assuming an SD of 7 percentage points, 50 subjects each for Treatment Sequence 1 and Treatment Sequence 2 are needed to have approximately 81% power to detect a 3 percentage point treatment difference in the mean absolute change in ppFEV1 from study baseline, after 28 days of treatment between VX-371 + HS

1006696
Parion Sciences Incorporated
CLEAN-PCD
SAP Version 1.0

and HS alone. Part A of the study will have approximately 87% power to detect a 4-percentage point change from baseline, after 28 days of treatment in ppFEV1 between VX-371 + HS and placebo. The power to detect a 3 percentage point difference between VX-371 and placebo is about 51%. The sample size estimate was based on 10000 simulation runs with an incomplete block design assuming no dropouts. In the simulation, the correlation between responses to the 2 treatments within a subject was assumed to be 0. Furthermore, a 2-sided significance level of 0.05 was used in the sample size determination with no multiplicity adjustment. The sample size also takes into consideration an assumed dropout rate of 10%.

Part A of the study will enroll approximately 150 subjects. However, as no therapeutic intervention study has previously been completed in PCD patients, the ability to enroll all 150 subjects is uncertain. Enrollment of less than 150 subjects will still provide useful information and could demonstrate an important difference between treatments. Enrollment into Part A will continue until approximately 150 subjects are randomized or the enrollment rate drops, despite suitable interventions, such that the planned enrollment cannot be achieved.

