4.1.2 Secondary Endpoints

- Change in QOL score as measured by the Quality of Life-PCD Questionnaire (QOL-PCD) and the St. George's Respiratory Questionnaire (SGRQ)^[1] from study baseline, after 28 days of treatment in Part A

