8.2 SECONDARY EFFICACY ENDPOINTS AND ANALYSES

Part A

SGRQ:

1006696
Parion Sciences Incorporated
CLEAN-PCD
SAP Version 1.0

The SGRQ will have three domains (Symptoms, Activity, Impacts) and Total for age groups ≥ 16 [REDACTED]

SGRQ total score for [REDACTED] will be analyzed using similar analyses as described in [Section 8.1 Part A](#) including mixed effect model and waterfall plot. Note that the mixed effect model will use study baseline for ppFEV1 as a baseline covariate. [REDACTED]

The summary statistics for the actual values and absolute changes from study baseline will be obtained for SGRQ total score [REDACTED].

QOL-PCD:

The QOL-PCD [REDACTED] - adult version, [REDACTED]

[REDACTED]
[REDACTED]
[REDACTED]
[REDACTED] Subjects aged 18 years and older at Day 1 of Part A will complete the Adult version of the questionnaire themselves at all visits. [REDACTED]

The Lower Respiratory Symptoms domain focuses on lung symptoms and the treatments evaluated in this study are targeted toward the lungs.

QOL-PCD Lower Respiratory Symptoms domain for each QOL-PCD questionnaire version will be analyzed using similar analyses for mixed effect model and waterfall plot as described in [Section 8.1 Part A](#). Note that the mixed effect model will use study baseline for ppFEV1 as a baseline covariate. [REDACTED]

1006696
Parion Sciences Incorporated
CLEAN-PCD
SAP Version 1.0

The summary statistics for the actual values and absolute changes from study baseline will be obtained for Lower Respiratory Symptoms domain for [REDACTED] QOL-PCD questionnaire [REDACTED].

Part B

For the Part B secondary efficacy endpoint, the analysis will be based on change from study baseline as well as change from Part B baseline.

SGRQ:

[figure not shown]
SGRQ total score [REDACTED] will be analyzed using ANCOVA model and waterfall plot as described in [Section 8.1 Part B](#).

The summary statistics for the actual values and absolute changes from study baseline and changes from Part B baseline will be obtained for SGRQ total score [REDACTED].

[figure not shown]
[figure not shown]
QOL-PCD:

QOL-PCD Lower Respiratory Symptoms domain for [REDACTED] QOL-PCD questionnaire [REDACTED] will be analyzed using ANCOVA model and waterfall plot as described in [Section 8.1 Part B](#).

[figure not shown]

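### The questionnaire visit window lets an early-termination SGRQ or QOL-PCD score from as early as Day 2 stand as the 28-day outcome

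*SAP*

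**What the plan says.** The Part A secondary endpoint in SAP 4.1.2 is the change in QOL-PCD and SGRQ "from study baseline, after 28 days of treatment in Part A". SAP 4.2.2 and Table 2 in SAP 8.5 word the Part B endpoint in the same way.

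SAP Appendix VI decides which record represents each visit. Most measures, including spirometry, use Table 8. SGRQ and QOL-PCD use "Table 9. Study windows for Day 1 and Day 29 only", which has no Day 15 row. Three rules in that appendix then apply:

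- After windowing, "all visits, including scheduled visits, unscheduled visits, and early termination visits will be eligible" to be the analysed record.
- If several records share a window, "the data closest to the scheduled day will be used", and ties go to the latest.
- A value is missing only if the window holds no measurement.

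Protocol Table 3-3 schedules both questionnaires at the early-termination (ETT) visit. On its timing, Protocol 8.1.5 says "an ETT Visit should be scheduled as soon as possible after the subject decides to terminate study drug treatment". After that visit only the safety telephone call is planned, and it includes no questionnaire.

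Part A scores go into a mixed model like the one for ppFEV1. In Part B they "will be analyzed using ANCOVA model and waterfall plot as described in" SAP 8.1. SAP 6.3 allows no imputation beyond dates and individual QOL-PCD scores.

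**The concern.** A subject whose ETT visit falls on Day 3 contributes a Day 3 score as the 28-day result. The closest-day rule gives no protection, because it only chooses between records and the ETT score is normally the only one. The score is observed, so this is not imputation in the formal sense, but it acts like carrying an early score forward.

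The same subject is treated in opposite ways on the two endpoints: the questionnaire score counts at Day 29 and the ppFEV1 from the same visit does not. The visible text gives no reason for the difference.

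Early stoppers may be those who tolerate the inhaled solution poorly. If early stopping differs between treatments, scores taken after a few days of dosing enter the 28-day means unequally and can move the comparison in either direction.

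**Working it through.** The plan gives no figure of its own on this point, so the check has three parts: the windows, the rule applied to example records, and the size of the effect.

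**1. Windows labelled Day 29 (SAP Appendix VI)**

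| Period | Table 8 (ppFEV1) | Table 9 (SGRQ, QOL-PCD) |
|---|---|---|
| 1 and 2 | Day 23 to 36: 36 − 23 + 1 = 14 days | Day 2 to 36: 36 − 2 + 1 = 35 days |
| 3 | Day 23 to 36 | Day 2 onward, no upper limit |

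The extra days are Days 2 to 22: 35 − 14 = 21, or 21/35 = 60% of the Table 9 window. Table 8 assigns all of them to Day 15.

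**2. Rule applied to record days within Period 1 or 2**

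| Records on days | Day 29 value, Table 9 | Day 29 value, Table 8 |
|---|---|---|
| 3 | Day 3 | missing |
| 10 | Day 10 | missing |
| 22 | Day 22 | missing |
| 10 and 29 | Day 29 | Day 29 |
| 3 and 37 | Day 3 | missing |

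**3. Dilution of VX-371 in HS versus HS in Part A**

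Inputs from SAP 3.5.1: 50 subjects in each of Sequences 1 and 2, and 10% dropout. From SAP 8.1: treatment and period as fixed effects, compound symmetry (the baseline covariate is left out here). Assumptions: every dropout stops early and has a score; half stop in each period; the effect builds linearly, so a Day d score carries d/28 of it.

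Per sequence, m = 0.05 × 50 = 2.5 subjects stop in each period. That leaves c = 50 − 2.5 = 47.5 with scores in both periods and m = 2.5 with a Period 1 score only. With within-subject correlation ρ, the model combines two estimates:

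- within-subject, variance σ²(1 − ρ)/c, in which a share m/(2c) of the effect rests on early scores;
- Period 1 only, variance 2σ²/m, in which all scores are early.

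Inverse-variance weighting gives the effective early share f = [m/(2(1 − ρ)) + m/2] / [c/(1 − ρ) + m/2]. Dilution is f × (1 − d/28). The factor 1 − d/28 is 0.821, 0.643 and 0.464 for d = 5, 10 and 15.

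| ρ | f | Day 5 | Day 10 | Day 15 |
|---|---|---|---|---|
| 0 | 2.5/48.75 = 5.13% | 4.2% | 3.3% | 2.4% |
| 0.5 | 3.75/96.25 = 3.90% | 3.2% | 2.5% | 1.8% |
| 0.8 | 7.5/238.75 = 3.14% | 2.6% | 2.0% | 1.5% |

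At ρ = 0, a dropout rate of 5% gives 2.1%, 1.6% and 1.2%, and a rate of 15% gives 6.4%, 5.0% and 3.6%. As a ceiling, if all 10% stop on VX-371 in HS, then at ρ = 0 f = 10% and dilution is 8.2%, 6.4% or 4.6%. At ρ = 0.5 the same ceiling is 6.2%, 4.8% or 3.5%.

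**4. Intolerance on one treatment**

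Assume that 5% of one treatment's SGRQ scores are early and 10 units worse (assumed; range 5 to 20). Its raw mean moves 0.05 × 10 = 0.5 units (0.25 to 1.0). Under the planned model the shift is f × 10, which is 0.51 at ρ = 0 and 0.39 at ρ = 0.5. For scale, Protocol 8.2.3 says: "A minimum change in score of 4 units was established as clinically relevant after patient and clinician testing". The raw shift is 0.5/4 = 13% of that (6% to 25%).

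**The case against.** The wide window can be defended. The analysis-set text in SAP 5.3.1 uses a period's data once the subject has taken one dose in it, and SAP 6.3 says observed data will be used. No Day 15 questionnaire is scheduled, so Table 9 is a natural rule for measures taken only at Day 1 and Day 29. The choice is pre-specified, and nothing requires the secondary endpoints to share the ppFEV1 window.

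The narrower window also has a cost. If early stoppers do badly on a treatment, their poor scores are real outcomes. Removing them relies on dropout at random, which is least plausible for these subjects. The 0.5-unit shift is a bias only if their unseen 28-day scores would have been better.

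The size is small as well. The 10% is a sample-size allowance, not a rate of early stopping on treatment. A dilution of 4.2% of a 4-unit effect is 0.17 units. Protocol 9.5 asks early stoppers to keep returning for assessments. Redacted text in SAP 8.1, 8.2, 8.5 and Appendix VI may hold a sensitivity analysis.

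Much of this stands: the effect is modest, exclusion can be selective, and a hidden sensitivity analysis cannot be ruled out. It does not remove the mismatch. The analysis-set and observed-data rules decide which data may be used; they do not turn a Day 3 score into a 28-day score. Protocol 9.5 refers back to 8.1.5, which plans only the ETT visit and the call. If keeping early stoppers was the intention, the visible text does not say so, and ppFEV1 does not follow it.

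**Conclusion.** The concern holds. A lone ETT score from Day 2 to Day 22 becomes the analysed Day 29 value for SGRQ and QOL-PCD, which does not fit the stated endpoint and is the reverse of how ppFEV1 from the same visit is handled. Dilution of the VX-371 in HS versus HS difference is about 1.8% to 4.2% for correlations of 0 to 0.5, with a ceiling of 8.2%. A 10-unit intolerance decrement would move the treatment comparison by 0.39 to 0.51 units under the planned model.

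These sizes rest on linear build-up, on every dropout stopping early with a score, and on an assumed decrement. Stopping after Day 22, leaving during washout or leaving without a score would reduce them. Only the secondary endpoints are affected. The missing upper limit in Period 3 matters little, because no later questionnaire is planned. The change is worth making before database lock, although it is unlikely to decide the trial.

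**What to change.** For SGRQ and QOL-PCD, use the Table 8 Day 29 window (after Day 22, up to Day 36) in all three periods for the main analysis. Summarise earlier ETT scores separately by treatment, with their number and study day. Run the present Table 9 mapping as a sensitivity analysis. If the redacted text already contains a sensitivity analysis of these records, only the main window needs to change.

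In Part A, missing Day 29 scores are then handled by the mixed model as for ppFEV1. In Part B, those subjects leave the ANCOVA, again as for ppFEV1.

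The cost is one SAP table and one extra run. The downside is that a few early stoppers leave the main questionnaire analysis, including those who stop in Period 1 with no other post-baseline score. That loss may itself be selective, and the sensitivity analysis shows whether it matters.
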